1.2.2.7 Drug-Related Deaths

Based on reports from the safety database as of June 30, 2009, there have been reports of death (approximately 1% [35/3800]), deemed by the investigator as possibly related to the administration of study drug. The most common cause of drug related deaths was GI perforation. Other causes included multiorgan failure, sepsis, hypotension, acidosis, and adult respiratory distress syndrome. For details on all drug-related deaths, refer to the current version of the Ipilimumab Investigator Brochure.

1.2.2.8 Safety of 10 mg/kg Multiple Doses

Based on a review of the program-wide SAE data as previously reported, evidence had suggested that ipilimumab-associated irAEs were dose dependent in frequency, and higher irAE rates had been observed at 10 mg/kg than at lower doses of ipilimumab. Subsequently, this dose-dependent effect was further demonstrated in CA184-022 in which three dose levels of ipilimumab were studied, including 0.3 vs. 3 vs. 10 mg/kg. Table 3 summarizes the overall irAE frequencies by dose from CA184-022 based on safety data from the locked clinical database.

Table 3. Summary of Immune-Related Adverse Events (irAEs) by Treatment Groups – Treated Subjects (CA184-022)

	Number of Subjects (%)		
	Ipilimumab		
	0.3 mg/kg (N=72)	3 mg/kg (N=71)	10 mg/kg (N=71)
Overall irAEs	26.4	64.8	70.4
Grade 3-4	0	7.0	25.4
GI irAEs	16.7	32.4	39.4
Grade 3-4	0	2.8	15.5
Hepatic irAEs	0	0	2.8
Grade 3-4	0	0	2.8
Endocrine irAEs	0	5.6	4.2
Grade 3-4	0	2.8	1.4
Skin irAEs	12.5	45.1	46.5
Grade 3-4	0	1.4	4.2

1.2.2.9 *Neuropathies*

Isolated cases of motor neuropathy of an autoimmune origin have been reported among patients treated with ipilimumab. Three cases have been diagnosed as Guillain-Barre syndrome (GBS), two of which were considered study related. In both cases, the GBS was atypical in nature and more clinically resembled polyneuritis. As of 30 June 2009, 27 cases of neuropathy SAEs have been reported. Of these, 22 were assessed as unrelated to study therapy because alternative etiologies, including brain metastases, spinal cord compression, arterial thrombosis, or platinum-base chemotherapy were identified in almost every case.

1.2.3 Clinical Efficacy of Ipilimumab

Treatment with ipilimumab has demonstrated clinically important and durable tumor responses in several malignancies including melanoma, prostate cancer, and renal cell carcinoma. The most extensively studied tumor type has been malignant melanoma and the principal demonstration of the efficacy of ipilimumab at the 10 mg/kg dose comes from 3 Phase 2 multicenter trials in 487 subjects with advanced melanoma: CA184022, CA184008, and CA184007¹⁴.

The overall survival (OS) results from these 3 completed primary Phase 2 studies are presented in Table 4

Table 4 Updated Overall Survival Results for 3 Primary Studies in Advanced Melanoma (as of 09-Mar-2009)

Parameter	CA184022	CA184008	CA184007	
	All Randomized	All Treated	All Randomized ^a	
	Ipilimumab 10 mg/kg N = 72	Ipilimumab 10 mg/kg N = 155	Ipilimumab 10 mg/kg + Placebo N = 57	Ipilimumab 10 mg/kg + Budesonide N = 58
OS, Median (Months)	11.43	10.22	19.29	17.68
95% CI (Months) ^b	(6.90, 16.10)	(7.59, 16.30)	(11.99, --)	(6.80, --)
Survival Rate at 1 Year (%)	48.64	47.22	62.41	55.87
95% CI (%) ^c	(36.84, 60.36)	(39.52, 55.11)	(49.37, 75.07)	(42.71, 68.79)
Survival Rate at 2 Years (%)	29.81	32.83	41.78	40.57
95% CI (%) ^c	(19.13, 41.14)	(25.37, 40.49)	(28.30, 55.46)	(27.12, 54.37)

^a Data are presented for the per-protocol mixed population of pretreated and previously untreated subjects.

^b Based on Kaplan-Meier estimation and CI computed using the bootstrap method.

^c Median and associated 2-sided 95% CIs calculated using the method of Brookmeyer and Crowley.

Further details on clinical results can be found in the current version of the Ipilimumab Investigator Brochure.

1.2.4 Ipilimumab in Prostate Cancer Patients

Although Ipilimumab is a fully human anti-CTLA-4 IgG₁ monoclonal antibody approved in the US for the treatment of unresectable advanced melanoma, it was in fact first administered to patients with prostate cancer. In this initial trial, a single dose of ipilimumab at 3mg/kg given to patients with hormone-refractory prostate cancer resulted in a $\geq 50\%$ decline in PSA levels in 2 of 14 patients, and $<50\%$ decline in 8 others¹⁵. The two responders did not have measurable disease, but one developed grade 3 toxicity of an inflammatory nature (rash). Of the two other patients who had measurable disease at baseline that were evaluated by repeat radiographic imaging, neither demonstrated an objective response using the Response Evaluation Criteria in Solid Tumors (RECIST). This trial showed that a single 3mg/kg dose of ipilimumab is tolerated but also indicated the risk of treatment-related immune events.

Overall, there have been ten clinical trials that are exploring the use of anti-CTLA-4 antibodies in the setting of prostate cancer. As a result of the data from TRAMP mice that were treated with anti-CTLA-4 antibodies combined with other treatments, six clinical trials have explored combinations with other immune adjuvants (GM-CSF), cancer vaccines (GVAX and PROSTVAC), chemotherapy, radiation and anti-androgen therapy. Although the studies are too small to be definitive, these trials overall have noted declines in PSA and a low frequency of radiographic responses at doses of ipilimumab $\geq 3\text{mg/kg}$. Radiographic responses in prostate cancer can be difficult to detect because bone metastasis, which are common with prostate cancer, are difficult to measure. In a Phase I trial combining GM-CSF with escalating doses of ipilimumab, 22% of patients receiving ipilimumab $\geq 3\text{mg/kg}$ experienced a significant PSA response^{16,17}. At the time of this report, 1 patient had a partial objective response in liver metastases in accordance with RECIST. Combining cancer vaccines and ipilimumab would presumably improve anti-tumour activity by amplifying immune responses focused to relevant antigens as demonstrated in mice. In a trial investigating ipilimumab with GVAX, 5 of 28 patients who completed treatment had a $\geq 50\%$ decline in PSA, and 12 had stabilization of metastatic bone disease for extended durations (12 to 21 months)^{18,19,20}. PROSTVAC has also been combined with ipilimumab. In a randomized phase II trial, PROSTVAC alone significantly improved overall survival over placebo in healthy, well-performing patients with mAIPC²¹. In the combination trial, 5 of 9 chemo-naïve patients with mAIPC who received 3 or 5 mg/kg of ipilimumab plus PROSTVAC had $\geq 50\%$ declines in PSA²². Overall 14 of 30 patients at any dose level of ipilimumab (1, 3, 5 and 10 mg/kg) had some decline in PSA. Physical tumor shrinkage however was infrequent. Of the previous 9 patients, 4 had stable disease ≥ 6 months, and 2 had unconfirmed partial responses. Nine of 15 receiving 10 mg/kg of ipilimumab had stable disease ≥ 6 months. Despite limited numbers of noticeable tumor shrinkage, both GVAX and PROSTVAC with ipilimumab trials showed a significant number of patients with stabilization of their disease under combination therapy that can last for several months and manageable side effects. However, further studies are required to see if the combination is more effective than either ipilimumab or vaccine alone.

In a phase II trial that combined ipilimumab with radiotherapy, no difference in the number of patients who had a decline in PSA $\geq 50\%$ was seen between patients treated with ipilimumab alone (5 out of 16 chemo-naïve patients) versus the ipilimumab and radiotherapy (4 out of 15 chemo-naïve patients), and fewer patients in the post-chemotherapy group had a decline in PSA $\geq 50\%$ when treated with ipilimumab and radiation (1 out of 14)^{23,24}. In a randomized phase II

trial comparing ipilimumab at 3mg/kg alone versus ipilimumab plus a single dose of docetaxel showed a limited number of PSA responses: 2 of 23 patients treated with ipilimumab alone and 1 of 20 patients treated with the combination therapy²⁵. There was no objective radiographic response observed at the time. However, in a randomized phase II trial of ipilimumab and androgen ablation, patients treated with ipilimumab and androgen ablation were more likely to have undetectable levels of PSA by 3 months (55% vs. 38%)²⁶. Another human IgG₂ monoclonal antibody (tremelimumab, Pfizer) has been tested in a phase I trial in combination with androgen deprivation in patients with PSA-recurrent non-metastatic prostate cancer but the results are not currently available at the time of writing (www.ClinicalTrials.gov, Identifier: NCT00702923)²⁷.

Blocking CTLA-4 in patients with prostate cancer revealed tumour response patterns not previously appreciated in inbred mouse models. For example, a decline in PSA levels can occur immediately after treatment but also after a period of stable disease or even after disease progression. For early phase trials, which are designed to capture early endpoints, such as safety or PSA responses, not enough time may have elapsed to see objective tumour responses by RECIST. Even so, more patients achieve disease stabilization rather than tumour shrinkage by radiographic assessment. One potential explanation is that AIPC mostly metastasizes to the bone, and bone lesions, whether regressing or progressing, are notoriously difficult to measure with current radiographic techniques. On the other hand, these response patterns have been consistently observed in patients with measurable metastases in advanced melanoma²⁸, yet objective responses still remain low overall (~10%)²⁹. If tumour control is sustained, however, patients may live longer. Indeed, the median overall survival in the PROSTVAC combination trial is 31.8 months³⁰, a significant duration in mAIPC, and in pre-treated metastatic melanoma, CTLA-4 blockade significantly improves survival by 4 months over gp100 vaccine, despite no improvement in time to progression or progression-free survival⁷.

1.2.4.1 Rationale for 3 mg/kg Dose of Ipilimumab

Given this experience with CTLA-4 blockade in AIPC, two recent phase III trials have investigated ipilimumab in mAIPC with overall survival as the primary endpoint. The first study compared ipilimumab versus placebo in individuals with mAIPC who have not already been treated with chemotherapy. The second trial compared ipilimumab following radiation therapy versus placebo following radiation therapy in patients who have already been treated with docetaxel chemotherapy for mAIPC.⁴⁷ Both studies addressed as their primary endpoint whether patients live longer with CTLA-4 blockade than patients treated in the control arm.

While the second study in metastatic prostate cancer did not meet the primary endpoint of improving overall survival (HR=0.85, p=0.053), Ipilimumab demonstrated antitumor activity in other efficacy endpoints, including progression-free survival. More importantly, safety was evaluated for all treated patients (pts; N=393 for ipilimumab 10 mg/kg, N=396 for placebo) starting from first study dose and ending 70 days after the last study dose, including maintenance dosing. Any grade (Gr) irAEs occurred in 63.4% and 21.7% of patients in the ipilimumab and placebo arms, respectively. Most common Gr 3/4 irAEs were gastrointestinal (GI) (18.1%; mostly diarrhea and colitis). Deaths due to study drug toxicity, as per investigators, occurred in 4 patients (4, ipilimumab and 0, placebo).

Thus, based on the above safety data from the second phase III trial which showed severe irAEs, the most frequent being diarrhea and colitis, the dose of ipilimumab has been reduced from 10 mg/kg to 3 mg/kg.

Our trial design of studying sequential treatment with ipilimumab following SipT represents the schedule that is currently clinically feasible. No data are available as to whether the presence of ipilimumab within a patient may alter the SipT product. Because the SipT product has specific release criteria, SipT treatment will be completed prior to treatment with ipilimumab in order to not jeopardize the production of the SipT.

PSA decline of > 50% was chosen as a secondary endpoint of this study given the difficulty of evaluating prostate cancer patients radiographically. Metastatic disease is primarily unmeasurable and bone scans rarely show the improvement that would reflect response and clinical benefit. To include only patients with measurable disease would limit the applicability of this therapy to a very limited subset of patients. Although PSA decline is not a widely accepted surrogate endpoint, it is often used as the primary endpoint in clinical studies.

Results from efficacy studies of ipilimumab in advanced melanoma have shown both the 3 and 10 mg/kg ipilimumab doses are safe and effective. Ipilimumab was approved in US and Europe at a dose of 3 mg/kg in adults patients with advanced melanoma based on a phase 3 study in patients with previously treated melanoma (MDX010-20). Ipilimumab 10 mg/kg was used in a second registrational study in adult patients with previously untreated advanced melanoma and prolonged overall survival when combined with DTIC, versus DTIC alone (CA184-024). A randomized phase 2 study in advanced melanoma (CA184-022) suggested that 10 mg/kg ipilimumab was potentially more active and was associated with increased toxicities relative to 3 mg/kg dose. An ongoing phase 3 trial (CA184169) of 3 vs. 10 mg/kg ipilimumab will provide definitive answer regarding whether there is an optimal monotherapy dose in advanced melanoma.

The dosing interval for ipilimumab is based on the prior study which demonstrated drug levels \geq 10 mg/mL (a minimum level required for CTLA-4 blockade in pre-clinical models) for greater than 28 days. Four doses of ipilimumab given every 3 weeks were chosen because four doses have been given safely in other trials.

2 STUDY OBJECTIVES: PHASE II STUDY

2.1 Primary Objective

- Determine whether the timing of ipilimumab administration impacts PAP and PA2024-specific immune responses induced by SipT.

2.2 Secondary Objectives

- Assess the safety associated with giving ipilimumab either immediately following completion of SipT or delayed ipilimumab following SipT.
- Assess clinical activity of the combination therapy for each study arm in chemotherapy-naïve patients with metastatic CRPC.
- Determine whether the timing of ipilimumab administration impacts the immunomodulation of activated effector and regulatory T cells.

3 STUDY DESIGN

This is a non-comparative open-label randomized multicenter Phase 2 clinical trial administering ipilimumab following standard SipT treatment in patients with chemotherapy-naïve metastatic CRPC. Patients will be accrued at UCSF and MD Anderson. Patients are randomized so as to achieve uniform patient cohorts treated on each regimen. Twenty-seven evaluable patients will be required per treatment arm, and 54-66 prostate cancer patients will be required to complete this multicenter study. The study will assess for the immunogenicity and clinical activity of sipuleucel-T treatment followed by ipilimumab in chemotherapy-naïve patients with metastatic castrate resistant prostate cancer (CRPC).

All patients will be treated with standard SipT (Q2 wks x 3). Patients will be randomized within 2 weeks of their final dose of SipT to one of two arms:

Arm 1 (Immediate Treatment)

[figure not shown]
Ipilimumab Q3 wks x 4 started 1 day following the final dose of SipT.

Arm 2 (Delayed Treatment)

Ipilimumab Q3 wks x 4 started 3 weeks following the final dose of SipT.

Following this “induction” ipilimumab treatment, patients will then be followed monthly for 3 months and then quarterly (every 12 weeks) until disease progression. The definition of unacceptable toxicity is grade 3 or higher treatment-related toxicities (NCI CTCAE v4) excluding irAEs. Patients who experience an initial clinical responses to ipilimumab followed by subsequent disease progression will be offered reinduction treatment with ipilimumab.

Figure 1. Dosing Schema

^aRandomization will be stratified by site and will occur within 2 weeks prior to the final SipT dose.

3.1 Safety Analysis

Because SipT treatment is associated with minimal toxicity, and an active dose of ipilimumab has been established (no MTD has been defined) with tolerable side effects, we propose to perform a safety analysis with standard SipT treatment and the 3 mg/kg dose of ipilimumab. Twelve patients will be randomized to either of the 2 scheduling arms (immediate vs. delayed) (6 per arm). After randomizing the initial 6 patients to each arm, the frequency and grade of AEs will be evaluated.

3.2 Phase 2 Design

Once the ipilimumab dose is established for each study arm, the randomization between the immediate and delayed arms will resume accruing a total of 27 evaluable randomized patients per study arm.

Randomized patients treated in the phase I at the same dose used in the Phase 2 study will be included for immune response analysis; thus patients accrued in the randomized component of the Phase I trial can be included for analysis of the study objectives.

Once written informed consent is obtained and the patient has undergone screening and determined to be eligible for the trial, treatment with SipT will begin. The patient will be randomly assigned following the second dose of SipT to one of the two treatment groups in a 1:1 ratio using a block design to maintain a balance in treatment assignment. Randomization will be stratified by site (UCSF and MD Anderson). The randomization will be performed by the study statistician at UCSF. At the time of randomization, a unique patient study identification number will be assigned to each patient. This study identification number must be included on all submitted forms and specimens.

Patients will receive induction treatment with 4 doses of ipilimumab on a 21-day cycle. As durable disease stabilization and/or objective tumor response can be seen after early progression, it is recommended that, in the absence of dose-limiting toxicities, all four doses of ipilimumab be administered over the initial 12 weeks even in the setting of apparent clinical progression, providing the subject's performance status remains stable.

All subjects who enter the induction period, including those who may have discontinued treatment for drug-related AEs and/or who have evidence of clinical progression during the induction period, should obtain a 12-week tumor assessment.

Clinical progression warranting alternative anti-cancer treatment should be considered only in subjects whose overall tumor burden appears to be substantially increased and/or in subjects whose performance status is decreased.

3.3 Reinduction Treatment

Patients who experience a clinical response to treatment during the first 12 weeks of ipilimumab treatment, but then develop subsequent progression of their disease after the initial 12 weeks of ipilimumab and who have not experienced unacceptable toxicity (refractory Grade > 3 irAEs) can be offered reinduction therapy with ipilimumab with up to 4 doses Q3 wks at the same dose level.

Following discontinuation of study therapy, subjects will complete a 30-day off study visit and then enter into follow up. Subjects who discontinue ipilimumab treatments should be followed until death or closure of the study (whichever is first). Subjects who are no longer receiving ipilimumab because of clinical progression and who have switched to alternative treatment are not followed formally except to record the date of death.

[figure not shown]

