5.3.2 Ipilimumab Modifications

Ipilimumab doses that cannot be given on schedule due to treatment-related adverse events will be skipped. No dose adjustments or delay will be allowed for treatment-related adverse events. Decisions to skip an ipilimumab dose must be made on specified safety criteria. Treatment with ipilimumab will be skipped or discontinued if the subject experiences at least one adverse event, specified below, considered by the investigator to be “possibly”, “probably” or “definitely” related to ipilimumab treatment.

Study drug dosing will be skipped for the following treatment-related adverse event(s):

- Any \geq Grade 2 non-skin, treatment-related adverse event (including irAEs), except for laboratory abnormalities
- Any \geq Grade 3 treatment-related laboratory non-hematologic abnormality
- Any adverse event, laboratory abnormality or intercurrent illness that, in the judgment of the investigator, presents a substantial clinical risk to the subject with continued dosing

It is necessary to skip study drug dosing for the following adverse events:

- Any \geq Grade 3 skin related adverse event regardless of causality

Restart ipilimumab dosing if/when the adverse event(s) resolve(s) to \leq Grade 1 severity or returns to baseline within 2 weeks of the last ipilimumab dose:

If the *adverse event has resolved*, restart ipilimumab dosing at the next scheduled time point per protocol.

If the adverse event has not resolved in time for the next dose (3 weeks \pm 3 days), the next scheduled dose will be skipped and dosing will be resumed at the subsequently scheduled dose. *Withhold of ipilimumab for longer than 60 days after the scheduled dose will lead to permanent discontinuation. Toxicities, which cause dosing delays $>$ 60 days will be considered sufficiently serious to lead to permanent discontinuation (not allowing for re-induction).*

If $>$ 1 dose is expected to be skipped, the dosing schedule modifications must be discussed with the principal investigator prior to implementation.

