5.4.6 Discontinuation of Ipilimumab Treatment

The following treatment-related non-neurological adverse events require permanent discontinuation of ipilimumab:

- Any \geq Grade 2 eye pain or reduction of visual acuity that does not respond to topical therapy and does not improve to \leq Grade 1 severity within 2 weeks of starting therapy, OR requires systemic treatment.
- Any \geq Grade 3 bronchospasm or other hypersensitivity reaction.

- Any other \geq Grade 3 non-skin related adverse event with the exception of events listed below under “Exceptions to Permanent Discontinuation”.
- Any \geq Grade 4 laboratory abnormalities, except AST, ALT, or Total Bilirubin
- AST or ALT $> 5 \times$ ULN
- Total Bilirubin $> 3 \times$ ULN
- Any other \geq Grade 4 adverse event
- *Withhold of ipilimumab for greater than 60 days due to treatment related toxicity*
- Any adverse event, laboratory abnormality or intercurrent illness, which, in the judgment of the investigator, presents a substantial clinical risk to the patient with continued dosing.
- The development of progression in the global tumor burden and/or clinical deterioration of subject’s condition such that further benefit from ipilimumab dosing is unlikely or requires a change of therapy.

The following neurological adverse event requires permanent discontinuation of ipilimumab and defines unacceptable neurotoxicity:

- Any motor neurologic toxicity \geq Grade 3 regardless of causality
- Any \geq Grade 3 treatment related sensory neurologic toxicity

Please refer to the Appendices for specific treatment algorithms.

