7.3.2 Significant Adverse Events

An understanding of the expected toxicities of ipilimumab suggests that the definition of "significant adverse events" (SigAEs) should exclude manageable immune related adverse events (irAEs). However, IrAEs refractory to steroid treatment will also be considered SigAEs. To evaluate the frequency of immune toxicities, patients will be assessed at baseline and monthly for immune signs and symptoms.

Significant Adverse Event (SigAE) is defined by any of the following that are attributable to therapy:

- Any \geq grade 3 or 4 non-immune-mediated toxicity (with immune-mediated toxicities defined as all irAEs listed in the ipilimumab investigators' brochure to be considered immune and per judgment of the principal investigator for events unknown as immune related adverse events).

- Any ocular toxicity considered to be immune-mediated and requiring systemic steroids.
- Any grade 3 or 4 irAEs that cannot be reduced to grade 2 or below with systemic steroids.

The following events are excluded as SigAE:

- Any toxicity attributable to androgen deprivation therapy.
- Any endocrinopathy thought to be immune-mediated where clinical symptoms are controlled with appropriate hormonal replacement therapy.
- Hospitalization for \leq grade 2 events where the reason for hospitalization is to expedite evaluation rather than to treat the toxicity.
- These criteria apply for both hematologic and non-hematologic toxicities.
- Grade 4 laboratory-only abnormalities for uric acid, WBC, and components of the WBC count.

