APPENDIX 8: TREATMENT MODIFICATIONS IN RESPONSE TO IMMUNE-MEDIATED ADVERSE EVENTS

- The recommended dose of YERVOY is 3 mg/kg administered intravenously over 90 minutes every 3 weeks for a total of 4 doses

YERVOY (ipilimumab)–Dose Modifications		
ADVERSE REACTION	WITHHOLD YERVOY FOR ANY OF THE FOLLOWING:	PERMANENTLY DISCONTINUE YERVOY FOR ANY OF THE FOLLOWING:
Immune-Mediated Enterocolitis	Grade 2 enterocolitis	Grade 3 or 4 enterocolitis
Immune-Mediated Hepatitis	AST or ALT >2.5x ULN to ≤5x ULN or total bilirubin >1.5x ULN to ≤3x ULN	AST or ALT >5x ULN or total bilirubin >3x ULN
Immune-Mediated Dermatitis	Grade 2 dermatitis	Grade 3 or 4 dermatitis
Immune-Mediated Neuropathies	Grade 2 neuropathy	Grade 3 or 4 neuropathy

- Withhold YERVOY for any other moderate (Grade 2) immune-mediated adverse reactions or for symptomatic endocrinopathy until return to baseline, improvement to mild severity, or complete resolution, and patient is receiving <7.5 mg prednisone or equivalent per day
- Permanently discontinue YERVOY for:
 - Persistent Grade 2 adverse reactions or inability to reduce corticosteroid dose to 7.5 mg of prednisone or equivalent/day
 - Failure to complete a full treatment course within 16 weeks from administration of the first dose
 - Any severe (Grade 3) or life-threatening (Grade 4) adverse reactions, including any of the following:
 - Colitis with abdominal pain, fever, ileus, or peritoneal signs; increase in stool frequency (≥7 over baseline), stool incontinence, need for intravenous hydration for >24 hours, gastrointestinal hemorrhage, and gastrointestinal perforation
 - AST or ALT >5 × ULN or total bilirubin >3 × the ULN
 - Stevens-Johnson syndrome, toxic epidermal necrolysis, or rash complicated by full thickness dermal ulceration or necrotic, bullous, or hemorrhagic manifestations
 - Severe motor or sensory neuropathy, Guillain-Barré syndrome, or myasthenia gravis
 - Severe immune-mediated reactions involving any organ system
 - Immune-mediated ocular disease that is unresponsive to topical immunosuppressive therapy

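### The toxicity gate for reinduction in section 3.3 conflicts with the section 3 meaning of unacceptable toxicity and, for some immune-related events, with the permanent-stop rules in 5.4.6 and Appendix 8

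*Combined protocol and SAP*

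**What the plan says.** Unacceptable toxicity is defined in section 3, and identically in the synopsis: "The definition of unacceptable toxicity is grade 3 or higher treatment-related toxicities (NCI CTCAE v4) excluding irAEs". The same paragraph of section 3 says that patients with an initial response "followed by subsequent disease progression will be offered reinduction treatment with ipilimumab", and attaches no toxicity condition to that sentence.

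Section 3.3 sets the conditions for reinduction: a response in the first 12 weeks of ipilimumab, progression after that, and a toxicity condition. It covers patients "who have not experienced unacceptable toxicity (refractory Grade > 3 irAEs) can be offered reinduction therapy with ipilimumab", for up to four doses. It refers to no other toxicity rule.

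The stopping rules stand elsewhere. Section 5.4.6 opens one list with "The following treatment-related non-neurological adverse events require permanent discontinuation of ipilimumab". That list takes in any other event of at least "Grade 3 non-skin related adverse event with the exception of events listed below under" the heading for exceptions, and it does not set irAEs aside. Appendix 8 calls for a permanent stop for "Any severe (Grade 3) or life-threatening (Grade 4) adverse reactions, including any of the following", and its table names grade 3 or 4 enterocolitis.

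One sentence, in 5.3.2, ties a permanent stop to loss of reinduction. Toxicities that delay dosing by more than 60 days are "considered sufficiently serious to lead to permanent discontinuation (not allowing for re-induction").

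**The concern.** One term carries two meanings, and one of them is a safety gate. The section 3 meaning removes irAEs; the section 3.3 meaning consists only of irAEs. An investigator deciding on reinduction must choose between them, and neither was written to match the events for which the protocol ends ipilimumab for good.

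A patient could therefore meet the 3.3 conditions after an event for which 5.4.6 and Appendix 8 require a permanent stop. Two sites could resolve this differently. At stake is the safety of the individual patient and the consistency of retreatment between sites.

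The situation can arise within the plan. Section 3.2 asks for a 12-week tumor assessment even in patients who stopped for drug-related events, so a patient who has stopped can still be recorded as a responder. Section 5.4.5 reports that responses were maintained in patients who had been given corticosteroids and taken off ipilimumab.

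**Working it through.** The check is mainly textual: take types of event and apply each rule as written.

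| Event (treatment-related) | Unacceptable by section 3? | Unacceptable by section 3.3? | Permanent stop? |
|---|---|---|---|
| Grade 3 immune colitis that responds to steroids | No: an irAE | No: neither refractory nor above grade 3 | Yes: 5.4.6 and Appendix 8 |
| Grade 3 immune colitis refractory to steroids | No: an irAE | No if > is literal; yes if it was meant as at least | Yes |
| Grade 4 immune colitis refractory to steroids | No: an irAE | Yes | Yes |
| Grade 3 non-immune, non-skin clinical event with no exception | Yes | No: not an irAE | Yes |
| Grade 3 immune motor neuropathy | No: an irAE | No, taken literally | Yes, and 5.4.6 calls it unacceptable neurotoxicity |

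1. Rows 3 and 4 show that the two definitions do not overlap. What one includes, the other leaves out.
2. Row 1 shows the gap. The event requires a permanent stop, yet the gate is passed under either definition. This does not depend on the > sign, because the word refractory already leaves the event outside the gate.
3. The 60-day bar in 5.3.2 need not close the gap. By the study calendar, Arm 1 doses fall on days 1, 22, 43 and 64, so dose 4 comes 63 days (9 weeks) after dose 1. The interval is the same in Arm 2. Colitis that starts after dose 4 delays no induction dose. Appendix 3 gives a range of onset for grade 3-5 enterocolitis up to 13.4 weeks; if that is counted from the first dose (not stated there), some cases start after dose 4.
4. Other passages do not close it either. Section 5.2.1 mentions reinduction with no toxicity condition. Section 6.2.2 lists what ends therapy, reinduction included, and names no toxicity criterion, only progression, withdrawal of consent and physician discretion.

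For size, the documents give no rate for this combination. The nearest figure is Table 3 (CA184-022, described in section 1.3 as a melanoma study), 3 mg/kg, N=71. Grade 3-4 irAEs were 7.0% overall, made up of GI 2.8%, endocrine 2.8%, skin 1.4% and hepatic 0 (2.8 + 2.8 + 1.4 + 0 = 7.0). Applied to the planned 54 evaluable patients:

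- all grade 3-4 irAEs: 0.070 x 54 = 3.8
- GI only: 0.028 x 54 = 1.5

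These counts come before the requirement of a response and later progression. Section 3.3 does not define response, so take a PSA decline of at least 50% as a stand-in and assume independence from toxicity. For ipilimumab alone at 3 mg/kg, section 1.2.4 gives 2 of 14 and 2 of 23, pooled 4/37 = 10.8%. The highest combination rate quoted there is 5 of 9 = 55.6%.

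- at 10.8%: 3.8 x 0.108 = 0.4 for all irAEs; 1.5 x 0.108 = 0.16 for GI only
- at 55.6%: 3.8 x 0.556 = 2.1 for all irAEs; 1.5 x 0.556 = 0.8 for GI only

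**The case against.** The strongest reply is that a permanent stop means what it says. Neither 5.4.6 nor Appendix 8 makes an exception for reinduction. Section 3.3 is permissive: reinduction can be offered, not must be. Section 6.2.3 also requires withdrawal when the investigator judges that further treatment is not in the patient's interest. On that reading 3.3 only lacks a cross-reference. This stands to the extent that a reader who infers that the protocol authorises retreatment after a permanent stop goes too far. It does not remove the conflict. Section 3 says reinduction will be offered, 3.3 states its own toxicity gate, and 5.3.2 spells out the loss of reinduction for one kind of permanent stop only, which invites the inference that other stops do not carry it.

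A second reply is that many grade 3 irAEs fall outside the problem. That stands. The grade 3 item in 5.4.6 covers non-skin events only, and 5.4.6.1 excepts controlled endocrinopathies, ocular toxicity that responded to topical therapy and some local inflammatory reactions. Grade 3 or higher motor events, and treatment-related sensory events, are separately labelled unacceptable. Appendix 8 does not carry the skin exception, since its table permanently stops grade 3 or 4 dermatitis, so the affected set depends partly on which rule is read.

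A reader might also infer that 3.3 contradicts the definition of a significant adverse event in 7.3.2, which counts "Any grade 3 or 4 irAEs that cannot be reduced to grade 2 or below with systemic steroids". The threshold does differ if > is literal. But 7.3.2 feeds the accrual rule in 9.2.2 and the handling of early progression in 7.1.3.1, and no section makes it a condition for reinduction. It is a difference in threshold, not a contradiction of the gate.

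**Conclusion.** The point holds as an internal conflict in a safety gate. Unacceptable toxicity has two definitions that share no event, and for some irAEs that require a permanent stop, of which steroid-responsive grade 3 immune colitis is the clear example, neither definition bars reinduction. The documents do not settle whether the permanent stop prevails.

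The size is small: about 4 of 54 patients with any grade 3-4 irAE, or about 1.5 of 54 with a GI event, before the response and progression conditions. With those conditions, the illustration runs from 0.16 to 2.1 patients. This assumes that a melanoma rate at 3 mg/kg carries over to ipilimumab after sipuleucel-T, that PSA decline stands in for response, and that response and toxicity are independent. Section 1.2.2.6 suggests that immune toxicity and antitumor activity may be linked, in which case the lower figures are too low. The illustration does not discount further for patients who respond but never progress.

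Sample size, power and the primary week-20 antibody analysis are not affected. The matter should still be corrected, because one misreading would give further doses to a patient for whom another section ends the drug permanently.

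**What to change.** Give unacceptable toxicity one meaning across the synopsis and sections 3 and 3.3, and reconcile it with 5.3.2, 5.4.6 (including its neurotoxicity wording) and Appendix 8. If two concepts are intended, name them differently. Cross-refer 3.3 to 5.4.6 and Appendix 8. State explicitly whether a patient permanently discontinued under those rules can be offered reinduction. Confirm whether the > sign in 3.3 is as intended, and make the reinduction sentences in the synopsis, section 3 and 5.2.1 point to 3.3.

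Which clinical rule should apply is for the sponsor and investigators to decide; none is proposed here. The cost is a wording amendment with the local IRB approval that section 10.5 requires. No patients, visits or analyses are added.
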